A Comparison of Treatment Methods for Patients Following
Total Knee Replacement

University of Pittsburgh

PCORI Award Number: CER – 1310-06994

Study Principal Investigator: [name]

Trial Registration: ClinicalTrials.gov Identifier NCT02237911

08/31/2014

A Comparison of Treatment Methods for Patients Following Total Knee Replacement.

Study Protocol

Design Overview - This comparative effectiveness study is designed to combine patient-centered research questions with rigorous research methods that minimize bias and balance internal and external validity. The pragmatic randomized clinical trial was selected to compare the treatments in ways in which they are delivered in routine clinical practice, so improving generalizability when informing what interventions work best. This will be a three group, single blind, pragmatic randomized clinical trial to answer the question: “In patients at later stages post TKR, given their personal characteristics, what are the comparative effectiveness and harms of the interventions available to them, among individual outpatient rehabilitative exercise, community-based group exercise classes, and usual medical care, especially with regard to physical function and activity?” This study focuses on: (1) outcomes of physical function and activity, both genuinely important to patients, (2) identifying predictors of functional recovery, and (3) potential harms of comparators. The design is depicted in the Figure above. In short, patients post-TKR will be informed about the study by their health care provider or by public announcement. Screening for eligibility will be done in two phases; over the telephone using a questionnaire, and in-person history and physical exam. Following pre-intervention evaluation, subjects will be randomized to one of the 3 groups:

1) clinic-based individual outpatient rehabilitative exercise; 2) community-based group exercise classes; or 3) usual medical care. The usual medical care group will continue their usual care whereas the other two groups will exercise during 12 weeks.

Endpoint measures will be assessed prior to and after intervention (3 months), and 6 months after randomization. After the 6 months follow-up, subjects in the usual medical care group will be randomized to either clinic-based individual outpatient rehabilitation exercise or community-based group exercise.

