- For patient-reported function we will use the Western Ontario and McMaster Universities Osteoarthritis Index Physical Function Subscale (WOMAC-PF). The score at 3 months will be the primary end point. This instrument was developed based on patient input and is the instrument of choice to assess outcome post-TKR.⁵³ The WOMAC-PF consists of 17 items related to physical function. Each item is scored on a 5-point Likert-type Scale with descriptors from 0-4 (none, mild, moderate, severe, and extreme difficulty). Scores of each item are summed for a maximum total score on the WOMAC-PF of 68. Higher scores indicate worse functional limitations. Reliability and validity of this instrument have been established.⁵⁴⁻⁵⁶ Prior to choosing the WOMAC-PF as the primary outcome, we received input from patients. We asked for 15 patients post TKR to compare the WOMAC, the Lower Extremity Functional Scale (LEFS) and the Knee Outcome Survey (KOS). The patients observed that 4 activities of the LEFS (running on even ground, running on uneven ground, making sharp turns while running fast, and hopping) were not applicable as they are unusual and contra-indicated motions after TKR. They also noted that the focus on symptoms of pain and knee buckling of the KOS were not as relevant to them as the activities limitations queries in the WOMAC. Patients selected the WOMAC as the most patient-centered of the 3 instruments, but added that we should also test their true ability to perform tasks (see below).

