The primary outcome of this aim is the WOMAC-PF at 3 months.⁹¹ This analysis will use an intention-to-treat approach. We will analyze this aim using contrasts from a linear mixed models analysis for 3 and 6 month function controlling for baseline function and the randomization covariates (age, gender, BMI, physical function, ROM). We will first explore the intervention by time interaction, and then proceed to a main effects model with only group and time. Our primary interest is the 3 month comparison between the clinic-based individual outpatient exercise and the community-based exercise groups. The linear mixed models allow us to maximize the number of individuals used for the analyses as a person can contribute information at both time points, or just one time point. This analysis is advantageous to conducting a simple baseline adjusted ANCOVA at 3 months because persons missing 3 month data would not be included. The linear mixed model “borrows” information pertaining to the relationship between the 3 and 6 month outcomes such that persons missing either (but not both) can still be used in the analyses. To test if the improvements in outcomes are sustained, we will use contrasts from the linear mixed model at 6 months. For missing 3 and 6 month outcomes see missing data section.

For the battery of performance-based tests we will perform the analyses as described above, one for each measure. For these secondary outcomes we will use Hochberg’s step-up procedure to control the experiment-wise Type I error rate ($\alpha=0.05$),⁹² which otherwise would be inflated due to the multiple endpoints. Hochberg’s procedure is more powerful than Bonferroni adjustment and performs well when the number of endpoints is small and correlated with small to mid-size correlations. For this outcome we will also perform analysis using a composite score formed with unit-weighted z scores of constituent tests to provide a more stable measure of the subjects’ underlying functional performance.⁹³

Hypothesis 1.2- Subjects in Groups 1 and 2 will demonstrate increased physical activity as compared to Group 3.

Adjusted analysis for the outcome of physical activity will parallel the analyses described above for performance-based physical function. The outcomes of this hypothesis are real-time physical activity data captured by the SWM and self-reported physical activity from the CHAMPS questionnaire

PRINCIPAL INVESTIGATOR (LAST, FIRST, MIDDLE): [name]

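### The plan does not say which mixed model supplies the 3-month primary contrast and the 6-month contrasts, and gives no rule for dropping the group-by-time interaction

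*Combined protocol and SAP*

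**What the plan says.** The endpoint and its timing are clear. Under Outcomes, Physical Function, the plan says of the WOMAC-PF: "The score at 3 months will be the primary end point". The Sample Size section is built on that visit.

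The model is described under Data Analysis, Hypothesis 1.1, in four statements:

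- Source of the results: "We will analyze this aim using contrasts from a linear mixed models analysis for 3 and 6 month function", adjusted for baseline function and the randomization covariates.
- Model sequence: "We will first explore the intervention by time interaction, and then proceed to a main effects model with only group and time". No condition is attached.
- Primary comparison: "Our primary interest is the 3 month comparison between the clinic-based individual outpatient exercise and the community-based exercise groups".
- Durability: "To test if the improvements in outcomes are sustained, we will use contrasts from the linear mixed model at 6 months".

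The secondary outcomes inherit this analysis. For the performance tests: "For the battery of performance-based tests we will perform the analyses as described above, one for each measure". Under Hypothesis 1.2: "Adjusted analysis for the outcome of physical activity will parallel the analyses described above for performance-based physical function".

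The section on dropout and missing data does not name the model either.

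**The concern.** Two models are described, one with and one without the interaction, and the text then refers to the linear mixed model as if there were only one. Three readings are open:

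- **(a)** The interaction model supplies the visit-specific contrasts and the main-effects model is a summary. This raises no problem.
- **(b)** The interaction is dropped if it is not significant. The primary estimate then depends on a preliminary test, whose significance level is not given.
- **(c)** The main-effects model is final and supplies the contrasts. The 3- and 6-month contrasts are then identical.

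The choice matters only if the group difference changes between visits. The plan takes that possibility seriously, since it intends to test whether improvement lasts. The Design Overview says that "the other two groups will exercise during 12 weeks", so month 6 falls well after study exercise ends. The documents do not say what difference to expect then.

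If the difference does change, (b) pulls the two visits' contrasts towards each other whenever the interaction is missed. Under (c) the month-3 effect is not estimated, and whether benefit is sustained cannot be tested.

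**Working it through.** **1. The plan's own figure.** Inputs from Sample Size: 86 per exercise arm, difference 3.3, SD 7.7, two-sided alpha 0.05.

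- SE = 7.7 × √(2/86) = 1.174
- 3.3 / 1.174 = 2.81
- Power = Φ(2.81 − 1.96) = Φ(0.85) ≈ 80.2% (79.8% with the noncentral t)

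The stated 81% is reproduced to within about a point. It is a month-3 calculation and corresponds to the contrast from a model that keeps group-by-time.

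**2. What a main-effects model estimates.** Write d3 and d6 for the clinic v community differences at the two visits. With complete data and equal variances, a model with only group and time gives (d3 + d6)/2 at both visits, with SE = 7.7 × √((1+ρ)/2) × √(2/n). This is algebra and needs no assumption about effects.

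For d3 = 3.3 and d6 = 1.65 the estimate is (3.3 + 1.65)/2 = 2.475. At ρ = 0.5 the SE is 1.017 and power is Φ(2.475/1.017 − 1.96) ≈ 68%. At ρ = 0.7 the SE is 1.083 and power is about 63%.

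With the plan's attrition (10% at month 3, 15% at month 6), the month-6 numbers are 96 × 0.85 ≈ 82 and 48 × 0.85 ≈ 41. Month 3 then has weight about 0.52, and the estimate is 0.52 × 3.3 + 0.48 × 1.65 ≈ 2.5.

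**3. Simulation of the three readings.** Three groups, 86/86/43 at month 3 and 82/82/41 at month 6, SD 7.7 at both visits, known variance, 2-df interaction test at 5%, 400,000 draws. The assumptions not in the documents are the between-visit correlation (0.5–0.7), the month-6 effects and the effects over usual care. In every row below, clinic v community is 3.3 at month 3 and 1.65 at month 6. The scenarios differ in how that arises:

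- (i) clinic 5.2 and community 1.9 points better than usual care, both halving;
- (ii) clinic 8.5 and community 5.2, both halving;
- (iii) only one exercise arm changes (clinic 5.2 to 3.55, community 1.9 at both visits).

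| Analysis | Interaction detected | Month-3 estimate | Month-3 power | Month-3 CI coverage | Month-6 contrast significant |
|---|---|---|---|---|---|
| Interaction kept | n/a | 3.3 | 80% | 95% | 28% |
| (b), scenario i | 38–59% | 2.96–3.10 | 76% | 90–92% | 39–49% |
| (b), scenario ii | 74–93% | 3.18–3.27 | 79–80% | 93–95% | 30–36% |
| (b), scenario iii | 25–40% | 2.86–2.97 | 73–75% | 89–91% | 45–54% |
| (c) | n/a | 2.5 | 64–69% | 88–89% | same test as month 3 |

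Under (b) the month-6 contrast is significant more often than the 28% its own effect supports, because part of the month-3 effect is carried into it.

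**4. Error rates.** With no effects anywhere, (b) rejects 5.3–5.5% of the time. With no month-3 difference but 1.65 at month 6 arising in one exercise arm, the month-3 test rejects 9–11% under (b) and 11–12% under (c), against 5% with the interaction kept.

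**5. Baseline adjustment.** The planned model adjusts for baseline function. If baseline correlates 0.4–0.5 with follow-up (assumed), the residual SD is 7.06 to 6.67. Interaction detection and the estimates do not change. Month-3 power becomes 87–90% with the interaction kept, 81–90% under (b) and about 72–85% under (c).

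**The case against.** The best defence is that reading (a) is the natural one. The section asks for a comparison at 3 months and contrasts at 6 months, which a main-effects model cannot give separately. The sentence on model sequence does not assign any contrast to the main-effects model. Reading (c), which does the most damage, therefore fits the paragraph least well. That is fair, and the figures under (c) should not be taken as the expected loss. But the only sequence the plan states ends, without condition, at the main-effects model, and nothing says that this model is secondary.

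The second objection is that harm under (b) depends on the scenario. Sample Size expects a large effect of either exercise arm over usual care. Scenario (ii) matches that best, and there (b) costs almost nothing. With a 25% fade in scenario (i), at correlations 0.5 and 0.7, (b) has power 82% and 78% against 80%, with estimates 3.02 and 3.05 and coverage 93%. With constant effects (b) has 89% and 85%, so it can gain as much power as it loses. This stands, and it limits the size of the concern. It does not justify letting the data choose the model for the primary contrast.

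**Conclusion.** The concern holds. The plan fixes the endpoint, visit and primary comparison, but not the model that produces the result. If its stated sequence is followed to the end, it gives one number for two visits. If the sequence is read as a preliminary test, the primary estimate depends on that test.

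For the primary comparison the harm under (b) is modest: at most about 0.4 points (3.3 − 2.86 = 0.44) and 7 percentage points of power in the scenarios shown, with coverage down to 89%. The test of sustained benefit is affected more, and under (c) it is lost. These sizes rest on assumed month-6 effects, effects over usual care and between-visit correlations. That a main-effects model gives identical contrasts at both visits rests on no assumption.

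This is a cheap clarification, worth making before data are seen, and does not invalidate the design.

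**What to change.** In Data Analysis, Hypothesis 1.1, state one model: group, categorical time (3 and 6 months) and group-by-time, with the planned covariates, and the interaction kept whatever its p-value. Take the clinic v community contrast at month 3 as the primary result and the month-6 contrasts from the same model. Label any model with only group and time as a supportive estimate of the average effect. Say that the same rule applies to the performance tests and to the physical activity outcomes under Hypothesis 1.2.

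This takes one or two sentences and needs no new data or sample size. The price is the pooled model's extra power if effects are equal at both visits (86–90% against 80%, unadjusted). No stated power is lost, because the plan's 81% is already a month-3 calculation.

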Potential Predictors of Treatment Response- Variables at the baseline that we believe may be potential predictors of treatment response, in addition to physical function (described above) include:

- Demographics and Biomedical Characteristics such as age, gender, race, education, BMI, self-rated health (excellent, good, fair, poor, or bad), discharge placement, number of prior rehabilitation sessions, TKR technique, and surgeon experience will be collected.
- Medication prescribed and over-the-counter used for pain will be recorded in the medication form. We will record the current and highest dosage of any pain medication used during the last month.
- Comorbidity data will be gathered using the Cumulative Illness Rating Scale.⁶⁹ Subjects will be asked to indicate conditions with which they have been formally diagnosed by a physician in the past.
- Psychosocial Measures will include factors that our and other groups have demonstrated to be associated with physical function in knee OA and include:^{48,70-72} 1) Fear; 2) Anxiety; 3) Self-Efficacy; 4) Depression; 5) Coping. We hypothesize that patients with higher fear, anxiety, depression and catastrophizing coping along with low self-efficacy who participated in the community-based group exercise classes will be able to improve physical function, whereas the ones who participated in the individual outpatient exercise will not. Fear-avoidance beliefs will be measured by the Tampa Scale for Kinesiophobia.⁷³ Anxiety will be measured using the Beck Anxiety Index.⁷⁴ Self-efficacy will be measured by the Arthritis Self Efficacy Scale.⁷⁵ Depression will be assessed by the Center for Epidemiologic Studies Short Depression Scale.⁷⁶ Coping will be measured by the Coping Strategy Questionnaire.^{77,78}

PRINCIPAL INVESTIGATOR (LAST, FIRST, MIDDLE): [name]

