For Aim 2, we plan to assess predictors of response based on a minimum change score of 20% in BOTH the WOMAC-PF and the composite score of functional performance at 3 months, thus yielding a binary outcome. For this aim, we will have a combination of those initially randomized to one of the exercise arms and those in the usual care group who were later randomized to the exercise arms for a total of approximately 200. If the expected response rate ranges between 50% and 60%, we would be able to detect an odds ratio of 2.2 to 2.4 with 80% power assuming a binary predictor with 50% split in the sample. In addition, with approximately 100 responders, we will be able to accommodate 9 predictors in the multiple logistic regression based on rule of thumb guidelines for sample size in logistic regression (min of response/nonresponse/ (#predictors+1) \geq 10).

Data Analysis

[name] will oversee data analyses. We will evaluate the statistical properties of baseline and follow-up outcome measures, including potential outliers, normality and missing data. Measures of central tendency (means, medians, other percentiles) and dispersion (standard deviations, ranges) will be computed for continuous variables, whereas frequency distributions will be calculated for categorical data. Distributions of baseline characteristics will be compared between groups to assess effectiveness of randomization, and statistical or clinical differences will be adjusted in the analyses. Data transformations may be applied if needed and guided by clinical meaningfulness.

Hypothesis 1.1 - Subjects in Groups 1 and 2 will demonstrate better physical function as compared to Group 3.

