Hypothesis 2- A group of baseline biomedical and psychosocial measures will associate with treatment response.

Each subject will be classified as a responder or non-responder based on a minimum change score of 20% in BOTH the WOMAC-PF and the composite score of functional performance at 3 months, thus yielding a binary outcome. Baseline variables will be summarized separately for responders and non-responders. Unadjusted odds ratios will be estimated using univariate logistic regression. To consolidate potential predictors, we will test for collinearity among baseline variables that are associated with response. Baseline measures associated with response at the $p<0.15$ level in unadjusted models will be added to multivariable logistic regression models to assess predictors of treatment response. We will limit the number of predictors going into any one model to no more than one predictor per 10 responses (or 10 non-responses, whichever is less); if more variables are significant, the model will be limited to the most significant variables, after adjusting for those deemed a-priori to be clinically significant. We expect different predictors for each group. For example, patients with worse physical function and impairments (e.g., limited range of motion and muscle weakness) will do better with individual outpatient exercise whereas those with heightened psychosocial factors (e.g., anxiety and depressive symptoms) will respond better to group exercise in the community.^{48,70-72}

Exploratory Hypothesis- Adherence and co-interventions will be similar in all groups. The attrition rate and adverse events- mainly number of falls- will be lower in Groups 1 and 2 compared to Group 3.

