During our pilot study 100% of the patients completed the 2 month follow-up assessment;¹¹ however we are realistic and recognize that such retention rate is very optimistic for this study. Thus, in this study we estimate the attrition to be 10% at the 3 months follow-up. We also estimate the attrition to be 15% at 6 months, based on our pilot work and other studies with similar populations and timeframes. We will compare baseline characteristics between patients with and without the assessment at 3 and 6 months to assess potential biases in the complete case analysis. We will also try to obtain reasons for study drop out to assess the missing data mechanism (missing completely at random, missing at random, non-ignorable missingness). We will use several missing data methods for imputing data and re-analyze using intention to treat (as randomized) to assess the impact of missing data on our conclusions as recommended.⁹⁷ We

PRINCIPAL INVESTIGATOR (LAST, FIRST, MIDDLE): [name]

will first use multiple imputation (with M=10 imputations) which assumes the data are missing at random. Since the data could be missing not at random, we will use another approach of assigning the lowest observed scores for missing values differentially by treatment group (non-ignorable missingness). The approach assumes the missingness is directly related to the value of the missing data, i.e., the people who are missing data on function have worse function scores (did not come in for assessment because function was worse). Results of all approaches to missing data will be presented in the primary paper for our study. If our significance and interpretation of our treatment effect vary depending on the method of imputation, we will view any conclusions cautiously.

PATIENT POPULATION

Detailed reasoning of inclusion criteria is provided in Human Subjects.

Subjects will be included in the study if they underwent a unilateral TKR 2 to 4 months prior to study, are older than 60 years of age, experience functional limitation in daily activities (score in the WOMAC-PF of at least 9 points), *speak English sufficient to understand study instructions*, are willing to be randomized to one of the 3 treatment groups, and have medical clearance to participate in the study.

Subjects will be excluded if they:

- Have absolute or relative contraindications to exercise testing as established by the American College of Cardiology/American Heart Association;^{99,100}

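### Aim 2: baseline function is built into the 20%-change responder outcome and is also a candidate predictor of it, so the two are associated for reasons other than treatment, with unknown size and direction

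*Combined protocol and SAP*

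**What the plan says.** The Hypothesis 2 section defines the outcome: "Each subject will be classified as a responder or non-responder based on a minimum change score of 20% in BOTH the WOMAC-PF", together with the performance composite, at 3 months. The Aim 2 paragraph under Sample Size uses the same definition.

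The section on potential predictors says: "Variables at the baseline that we believe may be potential predictors of treatment response, in addition to physical function (described above) include", and then lists demographic, psychosocial and knee-impairment measures. Selection is one variable at a time: "Baseline measures associated with response at the $p<0.15$ level in unadjusted models will be added to multivariable logistic regression models". The number of predictors is capped by the count of responders or non-responders. Adjustment is foreseen for variables judged clinically important in advance, but none is named.

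Hypothesis 2 expects different predictors in each group. Its example is that "patients with worse physical function and impairments (e.g., limited range of motion and muscle weakness) will do better with individual outpatient exercise", while patients with more psychosocial burden are expected to respond better to group exercise. No arm-by-predictor test is specified.

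The Aim 2 set contains only people who exercised: those first randomised to an exercise arm plus "those in the usual care group who were later randomized to the exercise arms for a total of approximately 200". Entry requires a "score in the WOMAC-PF of at least 9 points", on a scale where higher is worse. The Hypothesis 1.1 model controls for baseline function. Hypothesis 2 does not say that its models do, and it does not mention regression to the mean.

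**The concern.** Two mechanisms tie baseline function to response without any difference in benefit.

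- **Regression to the mean.** A patient whose baseline score is high partly by chance tends to score lower at 3 months and is more easily counted as a responder.
- **The percent threshold.** The required fall grows with baseline: 20% x 9 = 1.8 points at the entry minimum, and 20% x 40 = 8 points at a score of 40. This makes response harder from a worse baseline.

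The two pull in opposite directions, and nothing in the plan shows which dominates. An unadjusted screen picks up the net result. Any variable correlated with baseline function takes on part of it. The set has no untreated patients against whom the movement could be judged. At stake is the Aim 2 message about who should be referred to which programme. Baseline function, or a correlate of it, could be reported as a predictor of response to treatment when it reflects only how response was scored.

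**Working it through.** **1. The plan's own figure.** With about 200 subjects, a 50% split (100 v 100), 80% power and two-sided alpha 0.05 (stated for the primary endpoint, assumed for Aim 2), a two-proportion calculation gives a detectable OR of 2.26 at a reference response rate of 50% and 2.39 at 60%. This reproduces the stated 2.2 to 2.4. A Wald approximation at 50% agrees: SE = sqrt(2/(100 x 0.5 x 0.5)) = 0.283, and exp(2.80 x 0.283) = 2.21.

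**2. Inputs for the artefact.** From the documents: SD 7.7 (Sample Size), entry at 9 or more (Patient Population), response as a fall of at least 20%. Assumed, because the documents do not give them: mean WOMAC-PF 15-25, baseline to 3-month correlation r, equal SDs at both times, and the same improvement d (0-5 points) for everyone. Only the WOMAC-PF criterion is used here.

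**3. Formula.** A patient with baseline B responds if follow-up is at most 0.8B. Given B, follow-up has mean (mu - d) + r(B - mu) and SD 7.7 x sqrt(1 - r²). Hence

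P(response | B) = Φ{ [0.8B - (mu - d) - r(B - mu)] / [7.7 x sqrt(1 - r²)] }.

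The coefficient of B in the numerator is 0.8 - r. Response rises with worse baseline if r is below 0.8, does not depend on baseline at 0.8, and falls above it.

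**4. Worked example** (mu = 20, d = 3, baseline 25 v 15).

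- r = 0.5, conditional SD 6.67. At 15: (12 - 14.5)/6.67 = -0.375, response 35.4%. At 25: (20 - 19.5)/6.67 = 0.075, response 53.0%. OR = (0.530/0.470)/(0.354/0.646) = 2.06.
- r = 0.9, conditional SD 3.36. At 15: (12 - 12.5)/3.36 = -0.149, response 44.1%. At 25: (20 - 21.5)/3.36 = -0.447, response 32.7%. OR = (0.327/0.673)/(0.441/0.559) = 0.62.

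Benefit is 3 points for every patient in both cases.

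**5. Simulation over the whole range** (scores rounded to integers, baseline 9 or more, 400,000 patients per setting), OR for the worse v better half of baseline:

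| Correlation | OR |
|---|---|
| 0.5 | 2.0-2.4 |
| 0.6 | 1.6-1.9 |
| 0.7 | 1.3-1.4 |
| 0.8 | about 1.0 |
| 0.85 | 0.7-0.8 |
| 0.9 | 0.5-0.65 |

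**6. Correlated variables.** A covariate with an assumed correlation of 0.5 with observed baseline, and no other link to outcome, had OR 1.29-1.52 at r = 0.5 and 1.11-1.19 at r = 0.7. With baseline forced into the model at r = 0.5, its OR per SD went from 1.26 to 1.00.

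**7. Measurement error separated from real change.** A second model used true score plus error, with true percent change unrelated to true baseline and an assumed mean of 18-26.

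- WOMAC-PF criterion alone: the OR runs from 1.12 at reliability 0.95 to 1.77 at 0.70. Baseline passes the p<0.15 screen in 17-20% of trials at 0.95 and 82-84% at 0.70, against 15% nominal.
- Both criteria, taking the absolute baseline composite as denominator (the plan does not define a percent change on a z-score): OR 1.16-1.56 by WOMAC-PF half and 1.20-1.67 by composite half.
- WOMAC-PF criterion alone, same 5-point change for everyone: OR 0.33-0.35 at reliability 0.95, about 1.0 at 0.80 and 1.37-1.42 at 0.70.

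**8. Between arms.** With two identically affected arms, a baseline-by-arm test on the responder outcome gave 4.0-6.2% false positives at alpha 0.05. Reading each of two identical arms of 100 separately (mean 20, effect 3 or 5 points), worse baseline was significantly associated with response in exactly one arm in about 50% of trials at r = 0.5, 39-42% at 0.6, 21-22% at 0.7 and 5% at 0.8. By symmetry, about half of these would fall in the individual-exercise arm.

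**The case against.** Three stronger readings are tempting, and the documents support none of them.

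- **That the artefact favours the plan's hypothesis.** A reader might infer this from the expectation about "patients with worse physical function and impairments". It holds only below a correlation of about 0.8. Above that the percent threshold dominates and worse function appears to respond less. The documents give neither a correlation nor a reliability figure.
- **That it creates a false difference between exercise arms.** The hypothesis is that worse function does better with individual than with group exercise. Regression to the mean acts alike in both randomised arms, and a formal interaction test keeps its error rate. What remains is that no such test is specified and different predictors are expected in each group, which invites arm-by-arm reading.
- **That the artefact is as large as the detectable odds ratio.** It reaches 2.0-2.4 only at correlation 0.5 with the WOMAC-PF criterion alone. A correlation that low over three months of recovery may include genuine differences in how patients change. Where error was separated out, the odds ratio did not exceed 1.77.

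It can also be said that the plan allows adjustment for variables chosen in advance, and that its Randomization section names physical function as prognostic. That is fair: baseline is not excluded, but it is not required either, and the screening models are unadjusted. Adjustment would in any case leave the coupling in baseline's own coefficient. Finally, judging predictors only by interactions would change the question of Aim 2 and cost power. That objection stands, and the responder outcome should be kept.

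**Conclusion.** The concern holds in a limited form. As written, Aim 2 can report baseline function, or a correlate of it, as a predictor of treatment response when the association comes from how response is scored. Under a uniform benefit the odds ratio could lie anywhere from about 0.5 to 2.4 for correlations of 0.9 down to 0.5. This rests on SD 7.7, an assumed mean of 15-25, approximate normality and the WOMAC-PF criterion alone. Baseline function's own odds ratio is therefore uninterpretable as a treatment predictor in either direction. No false between-arm difference arises by itself; the risk lies in comparing separate arm-specific results. The Aim 1 primary analysis is not affected.

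**What to change.** In the Hypothesis 2 section:

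- Keep the responder outcome, but force baseline WOMAC-PF and the baseline composite into every Aim 2 model, including the single-variable screening models.
- State that their own coefficients will not be interpreted as predictors of treatment response.
- Test the expectation of different predictors in each group with arm-by-predictor terms, not by comparing separate arm-specific results.
- Add a supporting analysis of the continuous 3-month WOMAC-PF and composite, adjusted for baseline.

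**Cost.** No new data are needed. The two forced terms use two predictor slots. The plan's rule gives 100/10 - 1 = 9 slots at 50% response and 80/10 - 1 = 7 at 60%, so seven or five remain, and the arm and interaction terms draw on these too. Interactions have much lower power. With four cells of 50 and 50% response, SE = sqrt(4/(50 x 0.25)) = 0.566, so the ratio of odds ratios detectable with 80% power is about exp(2.80 x 0.566) = 4.9, against 2.2 for a main effect. Baseline function could be claimed as a predictor only through its interaction with arm.
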